5.5 Treatment Assignment Procedures

Stratified random sampling will be performed using SAS Proc Plan to generating random sequences and dispensing one of the Alpha-Stim AID kits provided by the sponsor (50% of kits active, 50% sham) and coded with unique serial numbers.

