10 STATISTICAL ANALYSIS PLAN

10.1 Sample Size

G*Power 3.1 was employed to calculate the number of subjects needed per group to detect a large group differences, slightly less than a 1 standard deviation difference (Cohen's effect, size, $d=.80$) in the effect of daily CES treatment on emotional well-being and PBMC telomerase activity. Based on a one tailed superiority test of improvement (active > sham CES treatment) and an alpha = .05, 22 subjects per group are required to provide adequate statistical power (80%) for the analysis (Noncentrality parameter=2.59, Critical $t(40)=1.68$. To meet this criteria we will include 22 completed subjects per group.

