10.2.1 Primary Outcomes

One tailed t-tests for independent groups will be performed to test the hypothesis that active CES device will be superior to sham in decreasing the combined HAD score. This will be accomplished by Contrast analysis within the framework of a random effects general linear mixed effects (RE GLMM) model.

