12.3 Study Records Retention

Upon completion of the study, the coding key and all identifiers will be destroyed, rendering the data anonymous.

With subject permission, we may store specimen data with or without subject's name or identifying information for future use. Retention of blood specimens after the end of the study for use in future research must be granted permission from the subject on the ICF. Subjects will give permission on the ICF if they agree to keep their name and other identifying information with their specimens. See 11.4 for future use of stored specimens plan.

13 RESULTS:

13.1 Feasibility: This was a feasibility study, initially powered for a sample size of 44. We fell far below the recruitment goals, despite 2 years of recruitment, finding a lack of interest for this intervention from the desired patient population. Therefore we consider the feasibility goal to have been a failure. The results should be interpreted with caution as the study was likely underpowered and the real world acceptability of the intervention in the context of this study was not desirable enough to recruit participants.

[figure not shown]
13.2 Baseline values and demographics:

11 subjects completed the Sham treatment and 13 completed the active treatment. No baseline differences in age, body mass index, HAD anxiety, HAD depression, or telomere length were identified between subjects randomized to the sham or active device groups. Both groups had 5 Veterans. Two subjects did not have baseline BMI measured. 1 subject did not have sufficient sample to complete the Telomere length.

No baseline differences were noted in age, BMI, anxiety, depression between Veterans and non-Veterans (all $p > .05$)

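### Allocation is described as stratified but no stratum term is named in the analysis; adding one is a nearly free improvement if the strata are prognostic

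*Combined protocol and SAP*

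**What the plan says.** Section 5.5 (Treatment Assignment Procedures) is the only place that mentions strata: "Stratified random sampling will be performed using SAS Proc Plan to generating random sequences". It adds that the kits are split equally ("50% of kits active, 50% sham"). It gives no stratification factor, number of strata or block size, and section 4.4 (Randomization and Blinding) supplies none.

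For the primary outcome, which is the combined HADS score, section 10.2.1 begins: "One tailed t-tests for independent groups will be performed to test the hypothesis that active CES device will be superior to sham in decreasing". It then says that this will be done by "Contrast analysis within the framework of a random effects general linear mixed effects (RE GLMM) model". No fixed or random effect is listed. Sections 10.2.2 and 10.2.3 give one-tailed independent-groups t-tests for the biological and exploratory outcomes, with no model around them.

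The sample size in section 10.1 also rests on a plain two-group comparison ("Based on a one tailed superiority test of improvement"), with d = 0.80 and one-sided alpha 0.05. Its conclusion is that "22 subjects per group are required to provide adequate statistical power (80%) for the analysis".

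**The concern.** Stratified allocation balances the arms on the stratification factors. If a factor predicts the outcome, that balance removes its contribution to chance differences between the arms, so the treatment estimate is more precise than under unrestricted allocation. A two-group t-test does not know this: it leaves the between-stratum variation in its error term. The reported standard error is then larger than the true one, the test rejects less often than its nominal 5% under the null, and precision that the design has already paid for goes unused. In a small pilot that is worth recovering, provided the strata are real and prognostic.

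**Working it through.** **1. Inputs.** From section 10.1: d = 0.80, one-sided alpha 0.05, 22 completed subjects per group, stated noncentrality 2.59 and 40 degrees of freedom. From section 13.2: 13 active and 11 sham completers. Not in the documents: R². Assumption: one binary stratum of equal halves, balanced across arms, with R² from 0 to 0.30.

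**2. The plan's own figure.** For a two-group t-test with n per group, the noncentrality is d·sqrt(n/2) on 2n − 2 degrees of freedom.

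- n = 20: power 79.9%.
- n = 21: 0.80 × sqrt(10.5) = 2.592, df 40, critical t 1.684, power 81.7%.
- n = 22: 0.80 × sqrt(11) = 2.653, df 42, critical t 1.682, power 83.3%.

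The stated 22 reproduces to within one subject. The printed noncentrality and degrees of freedom belong to 21 per group, which does no harm. The calculation is unadjusted and takes no credit for stratification.

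**3. Mechanism.** Set the within-arm variance to 1. With strata balanced across arms, the true variance of the arm difference is (1 − R²)·2/n, while the unadjusted test estimates it as about 2/n. The standard error is therefore too large by 1/sqrt(1 − R²). At R² = 0.30 this is 1/sqrt(0.70) = 1.195. The effective threshold in true standard errors becomes 1.682 × 1.195 = 2.01, a normal tail of about 2.2%, close to the simulated 2.4% below.

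**4. With 22 per group** (100,000 simulated trials per setting):

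| R² | SE ratio | Type I, no term | Power, no term | Power, with term | Gain (points) |
|---|---|---|---|---|---|
| 0 | 1.00 | 5.1% | 83.3% | 83.3% | 0.0 |
| 0.05 | 1.03 | 4.6% | 83.7% | 84.7% | 1.0 |
| 0.10 | 1.05 | 4.1% | 84.5% | 86.7% | 2.2 |
| 0.20 | 1.12 | 3.2% | 85.4% | 89.6% | 4.2 |
| 0.30 | 1.20 | 2.4% | 87.1% | 92.9% | 5.8 |

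With the term, type I error stays at 5.0% to 5.2%. The noncentral t with effect d/sqrt(1 − R²) and one degree of freedom fewer agrees: at R² = 0.30 it gives 93.0%.

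**5. With 12 balanced per arm**, close to the 24 completers:

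| R² | Power, no term | Power, with term | Gain (points) |
|---|---|---|---|
| 0 | 59.8% | 59.7% | −0.1 |
| 0.10 | 60.3% | 63.7% | 3.4 |
| 0.20 | 60.6% | 68.2% | 7.6 |
| 0.30 | 60.8% | 73.4% | 12.6 |

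**6. Where the shortfall comes from.** At 13 and 11 with R² = 0, the noncentrality is 0.80 × sqrt(143/24) = 1.953 on 22 degrees of freedom, and power is 59.8%. Going from 22 per group to this size costs 83.3 − 59.8 = 23.5 points before any question of adjustment arises.

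**The case against.** The strongest reply is that the premise rests on one loosely worded sentence. Section 5.5 speaks of stratified sampling, not stratified randomisation, and the word may mean no more than equal allocation from a half-and-half stock of kits. The primary model lists no terms at all, so a stratum term is neither included nor excluded. Nothing is lost if the strata do not predict the outcome.

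Much of this stands, and it limits how strongly the point can be put. It does not remove it. The only tests the plan names are independent-groups t-tests, and in 10.2.2 and 10.2.3 they stand alone. A pre-specified primary analysis should not leave its terms to be guessed. Whichever way the wording of 5.5 is resolved, one of the two sections needs a change.

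Three stronger readings are tempting, and the documents do not support them.

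- *A reader might infer that the trial lost its planned power this way.* It did not. At 22 per group the unadjusted test has 83% to 87% power at d = 0.80. Power is lost only relative to an adjusted analysis.
- *A reader might infer that the reported p-value is suspect on this account.* The error described here is conservative, so it does not undermine the p of .013 in section 13.3.
- *A reader might infer from section 13.2 ("Both groups had 5 Veterans") that Veteran status was the stratum.* The documents do not say so. Sections 2.1 and 4.2 say non-Veterans were admitted later, because recruitment was difficult, and 13.2 reports no baseline difference in anxiety or depression between Veterans and non-Veterans. Nor is five of 13 against five of 11 balanced, so a calculation on that split depends on the sign of the Veteran effect. With one sign, unadjusted and adjusted power are about 56% and 64% at R² = 0.10, and 52% and 73% at R² = 0.30. With the other sign they are about 64% and 63%, and 69% and 73%. No conclusion should rest on those figures.

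**Conclusion.** The point holds conditionally, as a free improvement and not as an error that threatens the result. The plan describes stratified allocation and names no stratum term in any analysis. If the strata are prognostic and are omitted, the test is conservative, and the term would recover 0 to about 6 points of power at 22 per group, or 0 to about 12.6 points with 12 balanced per arm. Those ranges rest on an assumed R² of 0 to 0.30, a single balanced binary stratum and a true d of 0.80; with R² near 0 there is nothing to recover. The low power at 24 completers comes mainly from sample size, which section 13.1 already acknowledges.

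**What to change.** In section 5.5, name the stratification factor or factors. In sections 10.2.1 and 10.2.2, add a sentence such as: *The stratification factor(s) used in section 5.5 enter the model as fixed effects.* For 10.2.2 this means a linear model in place of the bare t-test. If allocation was not in fact stratified, delete the word *Stratified* from 5.5 and leave the tests unadjusted on this account.

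The cost is wording plus one degree of freedom per stratum level beyond the first. With one binary factor of no prognostic value, calculated power goes from 83.28% to 83.25% at 22 per group, and from 59.8% to 59.7% at 13 and 11.

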5.6 Subject Withdrawal

Study participation is voluntary and subjects have the right to withdraw from the study at any time. The investigator may terminate a subject's participation if necessary.

5.6.1 *Reasons for Withdrawal*

Subjects are free to withdraw from participation in the study at any time upon request.

An investigator may terminate a study subject's participation in the study if:

- Any clinical AE or SAE, laboratory abnormality, or other medical condition or situation occurs such that continued participation in the study would not be in the best interest of the subject.
- The subject meets an exclusion criterion (either newly developed or not previously recognized) that precludes further study participation.
- Non-compliance with study protocol

5.6.2 *Handling of Subject Withdrawals or Subject Discontinuation of Study Intervention*

An adverse events report will be collected from subjects who choose to withdraw from the study. Subjects will be required to return study device to research personnel.

In the event of an (S)AE, every effort will be made to obtain follow-up data on any subject who discontinued device treatment due to an (S)AE. To the extent possible, any withdrawn subject will be followed until the (S)AE has resolved.

6 STUDY INTERVENTION

6.1 Study Device Description

The study device is a commercially available cranial electrotherapy stimulation device that applies an electrical current to a subject's head to treat anxiety, depression or insomnia.

6.1.1 Acquisition

Study device will be supplied and shipped by sponsor after IRB approval.

6.1.2 Packaging

Study device comes complete with the following accessories:

- One set of Earclip Electrodes
- 256 Earclip Electrode Pads
- 15ml Alpha Conducting Solution
- Two AAA batteries
- Storage case
- AID DVD
- Neck lanyard
- Illustrated Owner's Manual (multi-lingual Owner's Manual also available)

Weight: 2.0 lbs

Dimensions: 9 x 8 x 2 in

6.1.3 Product Storage

Study device should be stored inside provided storage case. The device and additional provided accessories should be kept in a safe place for subject use only and away from water.

6.2 Preparation and Usage of Study Device

Study product: Alpha-Stim AID

- Place earclip electrode pads to earclip electrodes
- Attach earclip electrodes to CES device
- Wet each electrode with Alpha Conducting Solution

- Clip electrodes to ears
- Set device frequency to 0.5 Hz and 100 μ A
- Set current to maximum of 600 microamperes, or to a comfortable level on the head
- Set probe timer at 60 minutes
- Remove earclip electrodes from ears after 60 minutes
- Unplug earclip electrodes from device and dispose of electrode pads
- Store device and additional accessories in storage case

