Objectives:	We aim to use a CES (cranial electrotherapy stimulation) intervention to improve emotional well-being by reducing symptoms of anxiety and depression and to assess for changes in markers of cellular health - specifically, telomere length and telomerase activity
Study Design:	Randomized, double-blinded, sham controlled trial
Study Population:	18-40 year old males, with symptoms of mild to moderate anxiety and/or depression, in the absence of a psychotic disorder
Phase:	Pilot
Study Site:	UCLA Oppenheimer Family Center for Neurobiology of Stress and Resilience
Description of Intervention:	A commercially available cranial electrotherapy stimulation device that applies an electrical current to a subject's head to treat anxiety, depression or insomnia. Electrical stimulation will be applied via ear clip electrodes at the lowest setting (0.5 Hz, 100 μ A) for 1 hour daily for eight weeks. In the sham group, the electrodes attached to the device will be inactive.
Study Duration:	24 months
Subject Participation Duration:	8-10 weeks
Estimated Time to Complete Enrollment:	20 weeks

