4.4 Randomization and Blinding

This is a randomized, double-blinded, sham controlled study. The active and sham devices are identical in appearance and will only differ by the labeling of a unique serial number. In the sham devices, the electrodes attached to the device will be inactive. The subjects will be instructed that the device is set to a low level so that the current is not detectable but still effective. The current will not be detectable in both active and sham devices in order for adequate blinding to occur.

To ensure that the allocation of subjects to treatment is properly concealed, the PI and research personnel will not know which devices are active or sham. The sponsor will provide the code to determine which devices are active and which are sham. Code will be in a sealed envelope that will not be opened until the end of data collection.

Schematic of Study Design

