6.2.1 Dosage

The dose selection (device frequency of 0.5 Hz and 100 μ A) is based on previous positive studies of the device for anxiety, depression, and insomnia. The dose selected is not detectable by the subject, so that adequate blinding can occur.

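### Section 6.2 follows the 100 microampere setting with a step allowing up to 600 microamperes or a comfortable level, which conflicts with the single, undetectable dose on which blinding depends

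*Combined protocol and SAP*

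**What the plan says.** All references are to the combined protocol and SAP.

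- **Dose.** The Protocol Summary says "Electrical stimulation will be applied via ear clip electrodes at the lowest setting", given there as 0.5 Hz and 100 microamperes for one hour a day over eight weeks. Section 6.2.1 repeats 0.5 Hz and 100 microamperes and justifies that choice by earlier studies of the device.
- **Setting steps.** Section 6.2 has the step "Set device frequency to 0.5 Hz and 100" (microamperes). The next step is "Set current to maximum of 600 microamperes, or to a comfortable level on the head", and the one after that is "Set probe timer at 60 minutes".
- **Blinding.** Section 4.4 says "The current will not be detectable in both active and sham devices in order for adequate blinding to occur". Section 6.2.1 says "The dose selected is not detectable by the subject, so that adequate blinding can occur". For the sham arm, section 4.4 says "In the sham devices, the electrodes attached to the device will be inactive".
- **What participants are told.** Sections 4.4 and 7.2 have participants told that the device runs at a low level. Section 7.2 adds that this level should not be detectable, but does not itself tie this to blinding.
- **Outcome.** The primary outcome in section 3.2.1 is the combined HADS score, from a questionnaire that participants complete themselves at the visits.

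**The concern.** Two adjacent steps set the same parameter in different ways. One gives a single value. The other gives a ceiling of 600 microamperes or a level chosen by comfort. Choosing by comfort means adjusting until something is felt, or until it stops being unpleasant, and neither fits a current that is meant to be imperceptible.

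The consequence is not symmetric between arms. Sham electrodes deliver nothing, so a sham user who turned up the control would feel nothing. An active user who did the same might feel the stimulation and infer the allocation. With a self-reported primary outcome, knowledge of allocation can shift scores without any effect of the device. The active dose would also differ between participants, so the comparison would no longer be of one stated dose against sham.

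**Working it through.** This is mainly a comparison of texts. The only arithmetic is the size of the permitted departure from the dose.

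**Step 1: every place that states or describes the current**

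| Place | Current | Adjustable? |
|---|---|---|
| Protocol Summary | 100 microamperes, called the lowest setting | Not mentioned |
| 4.4 | Low level, undetectable in both arms | Not mentioned |
| 6.2, first setting step | 100 microamperes | No range given |
| 6.2, next step | Up to 600 microamperes, or a comfortable level | Implied |
| 6.2.1 | 100 microamperes, undetectable | Not mentioned |
| 7.2 | Low level that should not be detectable | Not mentioned |

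Only one line departs from the rest. The description of it as the lowest setting appears only in the Summary. No section uses the word fixed for the dose. That is an inference from a single stated value with no titration described anywhere.

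**Step 2: size of the departure**

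- Ratio: 600 / 100 = 6.
- Difference: 600 − 100 = 500 microamperes above the stated dose.

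**Step 3: can the two steps be reconciled?**

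- *As a ceiling only.* A ceiling of 600 still admits values above 100, and the alternative of a comfortable level is not a ceiling at all.
- *As a locked device.* Telling participants that the device is set to a low level suggests a preset. No section says that the control is locked or that the 600 microampere line does not apply.
- *As a staff-only step.* Section 6.2 does not say who performs each step. The surrounding steps (wetting and clipping the electrodes, removing them after an hour, discarding pads, storing the device) are tasks for each session, and daily sessions after the first take place at home.
- *As carried-over text.* This is the likeliest explanation. The following step refers to a probe timer, while the accessory list in section 6.1.2 has "One set of Earclip Electrodes" and no probe. This explains the line but does not remove it from the instructions.

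**Step 4: what would follow if the line were used**

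The documents give no current at which stimulation becomes perceptible, so it is an assumption that some value between 100 and 600 microamperes can be felt. The reference to comfort points that way. Section 2.3.1 also says that dizziness and headache occur most often at higher currents, which could be a further cue to allocation. On that assumption, sections 4.4 and 6.2.1 would no longer hold for an active user who raised the current. Sham users would be unaffected because their electrodes are inactive.

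**Step 5: would the recorded data show it?**

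The diary items listed in section 6.3 are start and stop times, duration and side effects. Current is not among them. The calls in section 6.3 check that instructions are being followed, but that section does not say which current the instructions specify.

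**The case against.** The strongest reply is that this is a drafting slip with an obvious intended reading. The Summary, section 6.2.1 and the preceding step of section 6.2 all give 100 microamperes, sections 4.4 and 7.2 describe a low level, and the probe wording marks the passage as borrowed. That much stands: the intended dose is not in doubt.

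The second reply is that use was supervised at the point where a setting would be taught. Section 7.2 has participants trained on the device, with the first one-hour treatment at the centre. Section 2.3.1 gives the purpose of that session as confirming tolerability. Section 5.6.1 allows withdrawal for non-compliance with the protocol. These controls lessen the risk. None of them states the setting, and compliance with the protocol is ambiguous when the protocol contains both instructions.

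The third reply is that section 6.2 may not be what participants were given. The Instructions for Daily Use are listed in the Supplemental Materials but not reproduced, and section 6.2 is not identified as that sheet. This also stands, and it keeps the consequence conditional.

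A reader might go further and infer that active users did raise the current, that the blind was broken, or that the HADS difference in section 13.3 reflects unblinding. The documents support none of these. They record no setting above 100 microamperes and no instance of unblinding.

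**Conclusion.** The inconsistency is real and lies in an operative instruction. Section 6.2 as written permits up to six times the dose given in the Summary and section 6.2.1, and it invites adjustment by sensation, contrary to the condition for blinding in sections 4.4 and 6.2.1. Section 7.2 is consistent with that condition but only describes what participants are told.

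The threat to blinding and to a uniform dose is conditional on three things: that the control could be adjusted, that the 600 microampere step was followed, and that some permitted current can be felt. The documents settle none of them. The intended dose is clear, but the current actually delivered is not stated. Any effect on the HADS comparison cannot be sized from the documents, and none is claimed. The sample size and power figures are unaffected.

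The point should be fixed: the correction is cheap, and the matter bears on both dose and blinding of the primary outcome. Confidence is high for the conflict in the text. It does not extend to any consequence for the results.

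**What to change.** 1. Delete the 600 microampere or comfortable-level step from section 6.2.
2. State in section 6.2 that the current is fixed at 100 microamperes and is not to be adjusted by the participant.
3. Make the Instructions for Daily Use agree.
4. Because section 13 already reports results, add a sentence saying which setting was used and whether participants could adjust it.
5. Only if they could, qualify the double-blind description in the Summary and sections 4.1 and 4.4, and add possible unblinding as a limitation on the HADS result in sections 13.3 and 14.

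The cost is one line removed, one sentence on the fixed setting, a check of the instruction sheet and one sentence on what was used. No visits, staff or new data are needed. Items 1 to 3 correct the document but cannot change what was delivered. Item 4 is the part that can still alter what a reader concludes.
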